• Official Title: Use of Two Dissolvable Therapeutics Under Removable Partial Dentures: Reported Effects on Denture Comfort, Retention, and Dry Mouth Conditions

• NCT Number: NCT05441527

• Document Date: May 28, 2024

Objective: The primary aim of the present study is to quantify the change in a patient's saliva buffering capacity when MI Paste and Biotene Dry Mouth Gel is used under a removable prosthesis.

Design: This is a randomized, case-crossover study (*ClinicalTrials.gov identifier-NCT05441527*). The study population consists of adult subjects (ages 18-99) had a removable prosthesis (e.g., partial denture, complete denture that was made at the University of Iowa College of Dentistry and Dental Clinics (primarily the Family Dentistry Clinic and the Prosthodontics Clinics) within the past 10 years. Subjects cannot have any of the following criteria: casein (i.e., protein found in milk or other dairy products) allergy, lactose intolerance, multiple food or cosmetic ingredient allergies in their health history, ill-fitting dentures that need to be remade or relined.

Methods: Consented subjects will be randomly assigned to Group A or Group B. Randomization will be done as 1:1, in which subjects will have a 50% chance of being assigned to Group A (i.e., use MI Paste during the first week, use Biotene Dry Mouth Gel during the second week) or a 50% chance of being assigned to Group B (i.e., use Biotene Dry Mouth Gel during the first week, use MI Paste during the second week). Once a subject completes using the first product, they will voluntarily complete the questionnaire and be instructed to switch to the next product. Once the subject completes the second product, they will voluntarily complete the questionnaire.

Statistical Analysis Plan: The primary outcomes are: (i) change from baseline in patient comfort for MI Paste as assessed by numerical scale, (ii) change from baseline in patient comfort for Biotene Dry mouth gel as assessed by numerical scale, (iii) change from baseline in retention for MI Paste as assessed by numerical scale, (iv) change from baseline in retention for Biotene Dry Mouth Gel as Assessed by Numerical Scale. Descriptive statistics will be conducted to depict all the variables in the study. A paired-sample t-test or a Wilcoxon signed-rank test as appropriate will be used to detect the difference in saliva buffering capacity between pre- and post-MI paste application. Moreover, McNemar's test or 4 Bowker's test of symmetry will be used to compare the denture fit and function and dry mouth relief between pre- and post-MI paste application. All tests utilize a significance level of 0.05, and statistical analyses will be performed using the statistical package SAS® System version 9.4 (SAS Institute Inc., Cary, NC, USA).

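### The Objective and the SAP name different primary endpoints, and the named tests cover the buffering aim for one product only and none of the SAP's four primary outcomes explicitly

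*Combined protocol and SAP*

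**What the plan says.** The Objective reads: "The primary aim of the present study is to quantify the change in a patient's saliva buffering capacity", and continues "when MI Paste and Biotene Dry Mouth Gel is used under a removable prosthesis". The primary aim is therefore one quantity, buffering capacity, for two products.

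The Statistical Analysis Plan begins differently: "The primary outcomes are: (i) change from baseline in patient comfort for MI Paste as assessed by numerical scale". The list then gives comfort with Biotene, retention with MI Paste and, fourth, "change from baseline in retention for Biotene Dry Mouth Gel as Assessed by Numerical Scale". Buffering capacity is not on the list.

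The SAP then sets out three pieces of analysis:

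- **Description:** "Descriptive statistics will be conducted to depict all the variables in the study".
- **A paired t-test or Wilcoxon signed-rank test:** to "detect the difference in saliva buffering capacity between pre- and post-MI paste application".
- **McNemar's or Bowker's test:** "used to compare the denture fit and function and dry mouth relief between pre- and post-MI paste application".

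The Official Title refers to "Reported Effects on Denture Comfort, Retention, and Dry Mouth Conditions". It does not mention buffering and does not say what is primary. Methods describes a questionnaire after each product. It mentions neither a baseline questionnaire nor a saliva measurement.

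**The concern.** A primary aim should be answered by a primary outcome. Here the stated aim has no primary outcome, and the four stated primary outcomes serve no stated aim. A reader of the final report could not tell from these documents whether a buffering result or a comfort and retention result was the planned test of the products. Either could be put forward as primary once the data are known, and nothing in the text would contradict it.

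The analysis section does not resolve the matter. The only test suited to a change on a continuous or ordered scale is attached to buffering, which the SAP does not call primary. The outcomes that the SAP does call primary have no test attached to them by name. Making the labels agree would therefore not be enough, because either set would still lack a complete inferential analysis.

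**Working it through.** The documents give no sample size, power or effect size, so there is no planned figure to reproduce. The check is a comparison of texts.

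**Step 1. Do the two primary sets overlap?**

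| Source | Quantity | Products |
|---|---|---|
| Objective | Buffering capacity | MI Paste, Biotene |
| SAP (i) | Comfort | MI Paste |
| SAP (ii) | Comfort | Biotene |
| SAP (iii) | Retention | MI Paste |
| SAP (iv) | Retention | Biotene |

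None of the 4 SAP primaries is the quantity in the Objective. No sentence ranks the sets or links them.

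**Step 2. Which of these quantities has a named inferential test?**

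| Quantity and product | Named test |
|---|---|
| Buffering, MI Paste | Paired t-test or Wilcoxon signed-rank |
| Buffering, Biotene | None |
| Comfort, MI Paste | None assigned explicitly |
| Comfort, Biotene | None |
| Retention, MI Paste | None assigned explicitly |
| Retention, Biotene | None |

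Buffering has a test for 1 of its 2 products, and the SAP primaries have an explicitly assigned test for 0 of 4.

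**Step 3. Could McNemar's or Bowker's test be meant for comfort and retention?** The SAP does not say whether either is part of fit and function. If both are, three facts remain. These tests are for paired categorical data, whereas the primaries are changes on a numerical scale. The sentence is limited to MI Paste, so it could reach at most outcomes (i) and (iii). Outcomes (ii) and (iv), both for Biotene, have no inferential test on any reading.

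**Step 4. Does any other text decide which set is primary?** The Official Title shares comfort and retention with the SAP list, but it also includes dry mouth, which is in neither primary set, and it designates nothing. Methods mentions a questionnaire after each product and no saliva measurement, yet the SAP's references to baseline and to pre- and post-application values show that earlier measurements are intended for both kinds of outcome. Neither source settles the question.

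**Step 5. Is the baseline defined?** Each subject uses one product in the first week and the other in the second. The documents do not say whether the baseline for the second product is the value before the study or the value at the end of the first week. The change is therefore undefined for the second-week product, whichever set is primary.

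**The case against.** The strongest reply concerns the analysis. The Objective aims to quantify a change, which is an estimation aim, and the SAP promises descriptive statistics for every variable. On that view nothing is left unanalysed, and a test for every outcome is partly a matter of preference. Much of this stands. A reader might infer that the named tests fit neither primary set, or that the primaries have no analysis at all. The documents do not support that. The paired test is assigned explicitly to buffering with MI Paste and suits it, and description covers the rest. The gap that remains is inferential: the SAP tests other items while naming no test for its own primaries, and it tests one product where the aim covers two.

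A second reply is that an aim and an outcome are different things and need not match word for word. This does not help, because the mismatch is in what is measured and not in wording.

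A third reply is that the harm is only a possibility. That is correct. A reader might infer that the primary endpoint was switched or selectively reported. The documents do not show this. They cite a trial registration, but its content is not part of them, and it may record which set was fixed. It would be equally wrong to infer from the silence of Methods that saliva was never measured, or from the title that the comfort and retention set is the true primary.

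**Conclusion.** Wrong as written. The Objective and the SAP name non-overlapping primary endpoints and nothing reconciles them. The size is a matter of count: no overlap among the 4 SAP primaries, an inferential test for 1 of the 2 products in the buffering aim, an explicitly assigned test for 0 of the 4 SAP primaries, and no test on any reading for the 2 Biotene primaries.

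The conclusion rests on the text alone and needs no numerical assumption. It does not depend on an error rate or on power. It does not extend to a claim about conduct: the documents fail to show which set was fixed prospectively, and that is all that can be said.

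**What to change.** State one primary definition in identical terms in the Objective and the SAP, and label the other outcomes secondary. It must be the definition that was fixed prospectively, not one chosen on the results.

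**If the SAP list stands:**

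- The Objective reads: *The primary aim is to quantify the change from baseline in denture comfort and in retention with each product; change in saliva buffering capacity is secondary.*
- The SAP adds: *Each of the four changes from baseline is analysed with a paired-sample t-test, with the Wilcoxon signed-rank test as a sensitivity analysis.* Naming one main test avoids leaving that choice open until the data are seen.
- The SAP says that the McNemar or Bowker sentence covers other items, so that no outcome has two competing analyses.

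**If buffering stands:** the four comfort and retention outcomes become secondary, and the paired buffering test is extended to the comparison before and after Biotene Dry Mouth Gel.

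**In either case:** state which measurement is the baseline for each product, including the one used in the second week. The documents do not give this, so none is proposed here. If the prospectively fixed primary was not measured, report it as planned but not assessed, and do not replace it silently.

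**Cost:** wording in the Objective and SAP, a small amount of extra analysis, and the loss of primary status for some outcomes.

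### The exclusion criteria admit a subject with one known allergy to a non-casein component of either product, and both sequences assign both products

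*Combined protocol and SAP*

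**What the plan says.** The eligibility rules are in the Design paragraph of the combined protocol and SAP. The allergy and intolerance exclusions are a casein "allergy, lactose intolerance, multiple food or cosmetic ingredient allergies in their health history". The only other exclusion listed is "ill-fitting dentures that need to be remade or relined".

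The Methods paragraph describes a two-period crossover with allocation to sequence: "Randomization will be done as 1:1". Group A will "use MI Paste during the first week, use Biotene Dry Mouth Gel during the second week"; Group B will "use Biotene Dry Mouth Gel during the first week, use MI Paste during the second week".

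Neither the protocol text nor the SAP text lists the ingredients of either product. Neither states an exclusion for hypersensitivity to product components in general, and neither describes an ingredient check before a product is used.

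**The concern.** An allergy exclusion in a product trial is meant to keep out people who are known to react to what they will be given. Here only the casein criterion is tied to a particular allergen. The wider criterion depends on how many allergies a subject has, not on whether any of them concerns a study product. It can therefore turn away a subject with two allergies unrelated to either product and admit a subject with one allergy that is directly relevant.

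What is at stake is the safety of that second subject, who would be asked to use the product for a week under a removable prosthesis. The crossover matters because no allocation avoids one of the products.

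**Working it through.** The documents give no figure to reproduce on this point. The check is a reading of the criteria, followed by tracing exposure through the two sequences.

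**Step 1: apply the exclusion list.** The last phrase of the allergy criterion can be read in two ways:

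- Reading 1 (the plain one): *multiple* qualifies both food allergies and cosmetic ingredient allergies.
- Reading 2: *multiple* qualifies food allergies only, so any cosmetic ingredient allergy excludes.

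Take a subject with well-fitting dentures and no lactose intolerance:

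| Allergy history | Reading 1 | Reading 2 |
|---|---|---|
| Casein | Excluded | Excluded |
| Two food allergies, neither relevant to a study product | Excluded | Excluded |
| One food-type allergy, not casein, to a component of a study product | Eligible | Eligible |
| One cosmetic-type allergy to a component of a study product | Eligible | Excluded |

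The third row is admitted on both readings. The fourth depends on the reading, so two members of staff screening the same subject could reach different decisions.

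**Step 2: look for another safeguard.** Lactose intolerance is an intolerance, not an ingredient allergy, and does not close the third or fourth row. The denture-fit criterion is unrelated. Nothing in the Methods or Statistical Analysis Plan paragraphs adds a screen.

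**Step 3: trace exposure.** Inputs, from the Methods paragraph: a 50% chance of each sequence, and both products in each sequence. For either product,

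P(assigned the product) = P(Group A) × 1 + P(Group B) × 1 = 0.5 + 0.5 = 1.

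Randomisation decides only the week in which the subject is assigned the product concerned. This is the probability of assignment under the plan. Actual use also depends on consent and adherence.

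**Step 4: ask which planned analysis is touched.** The Statistical Analysis Plan paragraph defines four primary outcomes, each a change from baseline within one product (comfort and retention, for each of the two). The tests it names compare the state before and after MI Paste. No test of one product against the other is planned, and no stated figure depends on the allergy criterion.

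**The case against.** Several points can fairly be made on the other side.

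- **Effect on results.** A reader might infer that a reaction to one product would bias the comparison of MI Paste with Biotene Dry Mouth Gel. The documents do not support this, because the SAP plans no such comparison. Even if one were made, lower comfort caused by a product is part of that product's effect in the people enrolled and is not in itself bias. Stopping use could leave data missing, but nothing in the documents allows its extent to be judged. This objection stands, and the point is confined to safety.
- **Ambiguous wording.** *Multiple* may not govern cosmetic ingredient allergies. That stands, and it narrows the gap to the third row of the table. It does not close the gap, and the ambiguity itself needs resolving.
- **Hazard not demonstrated.** Without ingredient lists, the documents cannot show that any non-casein component is a likely allergen, or that such an allergy would be found in a health history. That stands as a limit on size. The fault in the rule can be seen without the lists, because the rule counts allergies instead of asking whether they are relevant.
- **Material not seen.** Consent pages were removed from the text, and an allergy warning or clinic check may exist. A reader might infer that an allergic subject is certain to use the product. The documents support only that the subject is eligible and is assigned it. A warning elsewhere would lower the risk but would leave the criterion as it is.
- **Existing screening.** Casein allergy, lactose intolerance and multiple-allergy histories are already covered. This is true, and it is why few subjects are likely to be affected.

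**Conclusion.** The point holds as a safety gap in the eligibility wording. Applied as written, the criteria admit a subject with one known allergy to a non-casein component of a product that the subject will be assigned. On the narrower reading of *multiple*, the gap remains for a single non-casein food-type allergy. For any subject so admitted, assignment to the product concerned is 100% by design.

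The number of such subjects is probably small. That is a judgement: the documents give no sample size, no allergy prevalence and no ingredient list from which to calculate it. The conclusion rests on two assumptions: that the Design paragraph is the complete exclusion list, and that no separate ingredient check operates outside the text available. It does not call any planned test or stated figure into question.

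**What to change.** Amend the exclusion line in the Design paragraph in three respects:

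1. State that a known allergy or hypersensitivity to any component of MI Paste or Biotene Dry Mouth Gel excludes a subject on its own.
2. Keep the casein, lactose intolerance and multiple-allergy criteria.
3. State whether *multiple* applies to cosmetic ingredient allergies as well as to food allergies.

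The information needed is the health history on which the criterion already relies, read against the two products' ingredient lists. The documents do not say when, or by whom, that history is reviewed, so the amendment should say so. If a component check already exists in the consent or clinic procedures, the eligibility text should refer to it.

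The cost is one revised eligibility line, one comparison against two ingredient lists for each subject, and a few more exclusions. No analysis changes.

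### All four primary outcomes are changes from a baseline that is neither defined nor scheduled, and the named tests make no use of the randomised product order

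*Combined protocol and SAP*

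**What the plan says.** All of this is in the combined protocol and SAP.

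- **Design and Methods.** The study is described thus: "This is a randomized, case-crossover study". Subjects are allocated 1:1 to one of two product orders, one week per product. Group A takes MI Paste first and Group B takes Biotene first.
- **Assessments (Methods).** Two questionnaires are placed in time: "Once a subject completes using the first product, they will voluntarily complete the questionnaire and be instructed to switch to the next product", and then "Once the subject completes the second product, they will voluntarily complete the questionnaire". Nothing is scheduled before the first product. No saliva sampling time and no washout are stated.
- **Objective.** The aim is to quantify the change in "saliva buffering capacity when MI Paste and Biotene Dry Mouth Gel is used under a removable prosthesis", so both products are named.
- **Primary outcomes (Statistical Analysis Plan).** The first two are "i) change from baseline in patient comfort for MI Paste as assessed by numerical scale" and "ii) change from baseline in patient comfort for Biotene Dry mouth gel as assessed by numerical scale". The other two are the same pair for retention.
- **Tests (Statistical Analysis Plan).** A paired t-test or Wilcoxon signed-rank test is to "detect the difference in saliva buffering capacity between pre- and post-MI paste application". McNemar's or Bowker's test is to "compare the denture fit and function and dry mouth relief between pre- and post-MI paste application". All variables are also to be summarised descriptively.

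Neither the baseline nor the before-application value is defined. Group A and Group B do not appear in the analysis section. No test is named for Biotene, for one product against the other, or for period or sequence.

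**The concern.** A change score needs a reference value. Here every primary outcome is a change score and no reference is scheduled. For the product used first, the natural reference is a value taken before the study. For the product used second there are two candidates: that same value, or the value at the end of the first product. They estimate different things, and an analyst could choose between them after seeing the data.

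The second issue is separate. The trial randomises product order, but the named tests compare subjects with themselves before and after MI Paste. Anything that shifts scores between the reference and the later weeks then counts as an MI Paste effect. The comparison that randomisation protects, MI Paste against Biotene, is not planned.

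**Working it through.** The documents give no sample size, SD or effect size, so there is no planned figure to reproduce. The finding is textual, and the algebra shows what follows from it.

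**Count from the text.** Four of four primary outcomes are changes from baseline. No assessment is scheduled before the first product. Both named comparisons concern MI Paste only, and neither uses the randomised order.

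**Notation (all values assumed).** m and b are the MI Paste and Biotene effects. d1 and d2 are the time trends at the end of weeks 1 and 2, relative to enrolment. L is the fraction of the first product's effect still present at the end of week 2. The two orders are of equal size.

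**1. If an enrolment value exists.**

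MI Paste change measured from enrolment:
- Group A: m + d1
- Group B: m + Lb + d2
- pooled: m + Lb/2 + (d1 + d2)/2

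MI Paste change measured from the value just before MI Paste (enrolment in Group A, end of Biotene in Group B):
- Group A: m + d1
- Group B: (m + Lb + d2) − (b + d1) = m − (1−L)b + d2 − d1
- pooled: m − (1−L)b/2 + d2/2

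The difference between the two readings is Lb/2 + (1−L)b/2 + d1/2 = **(b + d1)/2**. It does not depend on L, and it equals b/2 only when there is no week-1 trend. For Biotene the gap is (m + d1)/2.

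With assumed m = b = 1 scale point and no trend:

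| L | From enrolment | From value just before MI Paste | Gap |
|---|---|---|---|
| 0 | 1.00 | 0.50 | 0.50 |
| 0.5 | 1.25 | 0.75 | 0.50 |
| 1 | 1.50 | 1.00 | 0.50 |

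For b = 2 the gap is 2/2 = 1.0 point.

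**2. If no enrolment value exists.** Group A has no questionnaire before MI Paste, so there is nothing to pool. Group B's change estimates m − (1−L)b + (d2 − d1). With m = b = 1 and no trend, this is 0, 0.5 and 1 at L = 0, 0.5 and 1. Two equally effective products with no carry-over would thus show no MI Paste change. The Biotene change would likewise rest on Group A alone.

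**3. Time trend.** With m = b = 0, the pooled before-after mean is (d1 + d2)/2 from enrolment, or d2/2 from the value just before MI Paste. The crossover contrast is half the difference between the groups' mean week-1-minus-week-2 differences:

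½[(m + d1 − b − Lm − d2) − (b + d1 − m − Lb − d2)] = (m − b)(1 − L/2)

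The trend terms cancel.

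*One illustration, all inputs assumed:* a paired t-test at two-sided 0.05, measurement SD 1, within-subject correlation 0.5 (paired-difference SD √(2 × 0.5) = 1), no product effect, a shift of 0.3 SD in both weeks, 5,000 simulated trials per row.

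| Total N | Rejects, from enrolment | Rejects, from value just before MI Paste | Rejects, crossover contrast |
|---|---|---|---|
| 20 | 26% | 10% | 4% |
| 40 | 47% | 15% | 5% |
| 80 | 75% | 25% | 5% |

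**The case against.** The strongest reply is that baseline, used once for both products, ordinarily means before any study product. A baseline was evidently intended, and on that reading there is no carry-over bias if nothing persists from the first week. This largely stands, and it is the reading the fix adopts. It still has to be written down, because the tests refer to the value before MI Paste, and in Group B the only scheduled questionnaire of that kind is the one after Biotene. For saliva a third reading is open: immediately before and after an application.

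A second reply is that the aim and outcomes concern change within each product, so no between-product test is expressly promised, and randomising the order spreads order evenly across products. That also stands, so the product contrast is proposed as an addition. But balanced order does not remove a trend from either product's mean change.

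A third reply is that descriptive statistics will cover Biotene. They will, but they are not tests, do not control for trend, and need the same missing reference.

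Two stronger conclusions might be inferred and are not supported:

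- *No baseline is taken.* The documents do not show this either way.
- *The plan as written biases the pooled MI Paste change by (1−L)b/2.* That needs an enrolment value for Group A, which the schedule does not contain, together with a different reference for Group B.

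**Conclusion.** The concern holds as a gap in the definition and scheduling of every primary outcome, together with an analysis that leaves the randomised order unused. From the scheduled assessments alone, no primary change can be computed for the full randomised sample. If an enrolment value exists, the choice of reference moves the pooled MI Paste change by (b + d1)/2. If none exists, only Group B contributes, and its change mixes both products' effects with any trend from week 1 to week 2.

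The formulas assume additive effects, equal groups and complete data. The sizes of b, m, L and the trend are not in the documents, so the scale-point figures and rejection rates show direction and scale only and do not predict this trial's error rates. The conclusion rests on the text. It should be corrected before analysis because it affects all four primary outcomes.

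**What to change.** 1. Schedule the questionnaire and saliva test before the first product and at the end of each week. Define the value before the first product as the single reference for both products in both groups, including for McNemar's and Bowker's tests.
2. Keep the within-product changes and add a crossover model for the week-1 and week-2 numerical-scale and saliva values, with product, period and sequence fixed and subject random. Report MI Paste minus Biotene with a confidence interval, and describe the changes from baseline as uncontrolled for time trend.
3. State the carry-over assumption. A week-1-only comparison adjusted for the enrolment value can serve as a sensitivity check.

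**Cost.** One enrolment assessment, which a change from baseline already presupposes, plus wording and slightly more analysis. If a baseline is already taken, documenting it settles item 1 at almost no cost. Carry-over is not removed: if both products carry over the same fraction, the contrast shrinks to (m − b)(1 − L/2), so a true 0.50 becomes 0.375 at L = 0.5 and 0.25 at L = 1. The week-1 comparison avoids this but is less precise. Its standard error is about √(2(1 + ρ)) times larger, that is √2.8 ≈ 1.7 to √3.6 ≈ 1.9 for an assumed within-subject correlation ρ of 0.4 to 0.8.

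If subjects were enrolled without a baseline, only MI Paste versus Biotene can be estimated, and the primary outcomes should be restated accordingly.

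### Comfort and retention changes are primary for both products, but the Biotene outcomes have no named test or interval and the MI Paste outcomes have no numerical test

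*Combined protocol and SAP*

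**What the plan says.** The Statistical Analysis Plan names four primary outcomes. The first is "i) change from baseline in patient comfort for MI Paste as assessed by numerical scale", and the third is the same for retention. The Biotene counterparts are "ii) change from baseline in patient comfort for Biotene Dry mouth gel as assessed by numerical scale" and "iv) change from baseline in retention for Biotene Dry Mouth Gel as Assessed by Numerical Scale".

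Three kinds of analysis follow:

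- Description: "Descriptive statistics will be conducted to depict all the variables in the study".
- A paired-sample t-test or Wilcoxon signed-rank test to "detect the difference in saliva buffering capacity between pre- and post-MI paste application".
- McNemar's or Bowker's test to "compare the denture fit and function and dry mouth relief between pre- and post-MI paste application".

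The level is set by "All tests utilize a significance level of 0.05". The plan gives no confidence interval, multiplicity rule, sample size or scale length.

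Two other sections bear on this. The Objective gives the primary aim as change in saliva buffering capacity with both products. The Methods describe one questionnaire after the first product and one after the second, and none before the first.

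**The concern.** Neither test sentence mentions Biotene, and neither mentions comfort or retention. An analyst who followed the text would test buffering capacity, which is not on the primary list, and would run no test on two outcomes that are.

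For MI Paste, the only route to a test is to treat comfort and retention as part of denture fit and function. That is a natural reading, since the title speaks of "Reported Effects on Denture Comfort, Retention, and Dry Mouth Conditions", but the plan does not say so. On that reading, outcomes defined as change on a numerical scale go to tests for paired categories.

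Two things are at stake. Half the declared primary outcomes would end without an inferential result. For the other half, whether a test is run at all depends on interpretation, and that choice could be made after the data are seen.

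**Working it through.** **Step 1. Match outcomes to analyses.** All entries come from the Statistical Analysis Plan.

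| Primary outcome | Description | Paired t or Wilcoxon | McNemar or Bowker | Interval |
|---|---|---|---|---|
| (i) Comfort, MI Paste | yes | no | only if fit and function includes it | none named |
| (ii) Comfort, Biotene | yes | no | no | none named |
| (iii) Retention, MI Paste | yes | no | only if fit and function includes it | none named |
| (iv) Retention, Biotene | yes | no | no | none named |

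A paired numerical test is named for 0 of 4 outcomes, a categorical test for at most 2 of 4, and any test or interval for 0 of the 2 Biotene outcomes. This step needs no assumption.

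**Step 2. What the categorical tests measure.** McNemar's statistic is (b − c)²/(b + c), where b and c count subjects who cross a single cut upwards and downwards. Bowker's statistic sums (n_ij − n_ji)²/(n_ij + n_ji) over all pairs of categories, with k(k − 1)/2 degrees of freedom: 10 for k = 5 and 55 for k = 11. Neither uses the size of a change and neither estimates it. On a 0 to 10 scale cut between 5 and 6, a rise from 1 to 5 counts as no change, and a rise from 5 to 6 counts in full.

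**Step 3. Illustration of the cost.** The plan gives no figure to reproduce, so every input is assumed: bivariate normal scores rounded and truncated to the scale, SD 20% of the scale range, a shift of 0.5 SD, correlation 0.5, 40 subjects, two-sided 0.05. Simulated power:

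| Test | 5-point scale | 11-point scale |
|---|---|---|
| Wilcoxon signed-rank | about 79% | about 85% |
| McNemar after a midpoint split | about 47% | about 54% |
| Bowker, uncollapsed, counting only non-empty pairs as degrees of freedom | about 29% | about 1% |

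The McNemar figures move by several points with the position of the cut and of the baseline mean. Part of Bowker's loss is conservatism in sparse tables: with no shift and 40 subjects it rejects in 1.7% of runs on 5 points and 0.1% on 11 points, not 5%.

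**Step 4. Error rate before and after the fix.** As written, at most two primary outcomes are tested, so the familywise error is at most 2 × 0.05 = 10%. With all four tested at 0.05 the bound is 4 × 0.05 = 20%; if the tests were independent it would be 1 − 0.95⁴ = 18.5%. Holm compares the smallest p-value with 0.05/4 = 0.0125.

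**The case against.** The strongest objection is that the premise is unsettled. If the Objective governs, buffering capacity is primary, comfort and retention are not, and the MI Paste measure already has a suitable paired test. This stands as a reason to reconcile the two sections. It does not remove the gap: the Objective also covers Biotene, and no test of buffering capacity is named for that product.

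A second objection is that description of some outcomes is legitimate. It is, and the descriptive sentence does reach the Biotene data. What the plan does not explain is why two products with equal standing on the primary list are treated differently.

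A third is that naming MI Paste alone may be a slip. Perhaps so, but it occurs in both test sentences. Adding Biotene to both would still leave comfort and retention without a numerical test.

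A reader might also infer stronger points that the documents do not support:

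- *Almost all power is lost.* The 1% figure needs an uncollapsed 11-point Bowker table. The plan also names McNemar's test and does not commit to that table or state a scale length.
- *The plan carries a 20% familywise error.* That bound arises only once four primary tests are added.
- *The randomised crossover is invalid without a product comparison.* The listed outcomes are within-product, so the unused randomised order is a mismatch of design and analysis and leaves no stated hypothesis unanswered.
- *Baseline for MI Paste in Group B is the value after Biotene.* The outcomes are worded as change from baseline, which points away from this.

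**Conclusion.** The concern holds in this form. By direct reading, the two Biotene primary outcomes have no named test or interval. The two MI Paste primary outcomes have no numerical test, and have a categorical one only if fit and function is read to include comfort and retention.

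The power loss is an illustration. It depends on an assumed scale, sample size, SD, correlation and shift, and on the broad reading of fit and function. Under those inputs it runs from a substantial loss with McNemar to a near-total one with uncollapsed Bowker on a long scale. The mapping defect stands without these figures and should be corrected before analysis.

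**What to change.** 1. Settle which outcomes are primary: reconcile the Objective's buffering-capacity aim for both products with the primary list, and with a buffering test that covers MI Paste only.
2. Confirm that a questionnaire was completed before the first product. If so, define baseline as that value in both sequences.
3. For all four primary outcomes, analyse change from baseline with the paired t-test or Wilcoxon signed-rank test already named, and report a 95% confidence interval. Label the results as uncontrolled before/after estimates.
4. Use Holm across the four tests, or state that they are unadjusted.
5. Keep McNemar's and Bowker's tests for categorical items other than the comfort and retention scores, for both products, as secondary. This avoids testing the same items twice.
6. If no baseline was collected, change from baseline cannot be estimated. The two planned questionnaires then support the within-subject MI Paste minus Biotene difference, adjusted for period: average the mean difference in Group A and the mean difference in Group B, with a 95% confidence interval. No washout is described, so state that carryover cannot be excluded, and that the contrast compares the two products without showing that either works beyond placebo. If a baseline exists, this contrast is an optional secondary analysis.

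The cost is revised SAP wording, a little more analysis and, if Holm is used, a stricter threshold. Without adjustment, the familywise error can reach 20%. Items 3 and 4 depend on the baseline questionnaire in item 2.
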